6.6.4.2 Laboratory Tests Changes Over Time

Laboratory test observed values and changes from baseline are summarized as continuous parameters over time at baseline and each scheduled analysis visit on treatment. Laboratory tests may include the following:

- Hematology: hemoglobin, platelets, INR, WBC, lymphocytes (absolute), and ANC;
- Hepatobiliary enzymes and measures of hepatic synthetic function: ALT, AST, and total bilirubin;
- Pancreatic enzymes and renal function tests: lipase colorimetric and creatinine.

Laboratory test observed values and changes from EOT are summarized analogously over time at EOT and each scheduled analysis visit during follow-up.

6.6.4.3 Select Laboratory Test Results

Select laboratory test endpoints are summarized as categorical parameters as follows for treated participants, unless specified otherwise:

- Confirmed creatinine clearance $< 1.0 \text{ mL/s/m}^2 \ (< 60 \text{ mL/min/1.73m}^2)$ using the Schwartz formula on treatment. Confirmed is defined as ≥ 2 consecutive values meeting the criteria on treatment.
- ALT normalization (i.e., ALT \leq 1 x upper limit of normal [ULN]) at EOT by baseline ALT category (all; ALT \leq 1 x ULN; ALT > 1 x ULN; not reported) on treatment.
- ALT normalization at EOS by EOT ALT category (all; ALT \leq 1 x ULN; ALT > 1 x ULN; not reported) during follow-up for follow-up participants.
- AST normalization (i.e., AST \leq 1 x ULN) at EOT by baseline AST category (all; AST \leq 1 x ULN; AST > 1 x ULN; not reported) on treatment.
- AST normalization at EOS by EOT AST category (all; AST \leq 1 x ULN; AST > 1 x ULN; not reported) during follow-up for follow-up participants.
- Potential Drug Induced Liver Injury (PDILI) on treatment or during follow-up, defined as concurrent (1) ALT ≥ 5 x minimum(baseline, nadir), and ALT ≥ 10 x ULN, and (2) total bilirubin ≥ 2 x ULN. Concurrent is defined as the total bilirubin elevation occurring within 30 days after the ALT elevation.

6.6.5 Vital Signs

Vital signs observed values and changes from baseline are summarized as continuous parameters over time at baseline and each scheduled analysis visit on treatment for treated participants. See Section 6.3.2.3 for parameters.

A by-participant listing of vital signs is provided for enrolled participants.

6.6.6 Physical Measurements

Age-adjusted physical measurements (i.e., HAZ, HAP, WAZ, WAP, BMIAZ, BMIAP) observed values and changes from baseline are summarized as continuous parameters over time at baseline

and each scheduled analysis visit on treatment and during follow-up for treated participants. See also Section 6.3.2.3.

A by-participant listing of physical measurements is provided for enrolled participants.

6.6.7 Pregnancy

A by-participant listing of pregnancy test results is provided for enrolled female participants.

6.7 PK Analyses

PK analyses are performed for each cohort separately, and not combined across cohorts.

PK analysis, reporting, and exclusion criteria follow the BMS PK Harmonization Document.⁵ Specific guidelines for exclusionary criteria for half-life and how other PK parameters are affected for exclusion are in Section 9 of this document, while conventions for handling concentrations < LLOQ are in Section 11 (i.e., for DCV, LLOQ = 2 ng/mL; for SOF, LLOQ = 5 ng/mL; for SOF metabolite (GS331007), LLOQ = 10 ng/mL).

6.7.1 Intensive PK at Day 10

Intensive PK is assessed for treated PK participants with intensive PK at Day 10.

6.7.1.1 PK Concentration

DCV plasma concentration at Day 10 is summarized over time using univariate statistics (i.e., n, mean, SD) at each nominal collection hour: 0 (pre-dose), 30 min, 1 (Cohorts 1 and 2 only), 2, 4, and 8.

Two graphs are also provided:

- Parallel line plots of individual DCV plasma concentration (linear and semi-log scales) versus actual collection time;
- Longitudinal plot of mean DCV plasma concentration (linear and semi-log scales) versus nominal collection time, with error bars representing ± one SD.

A by-participant listing of DCV plasma concentration is provided. Values excluded from the summary are flagged.

6.7.2 PK Parameters

Individual PK parameter values for DCV (see Table 6.7.2-1) are derived from plasma concentration versus time at Day 10 using non-compartmental methods or model-based approaches as needed. DCV PK parameter values are summarized using univariate statistics (i.e., n, mean, SD, geometric mean, coefficient of variation [%CV], median, quartiles, minimum, and maximum).

Table 6.7.2-1: PK Parameters

Parameter (Units)	Definition
Cmax (mg/mL)	Maximum observed plasma concentration

Table 6.7.2-1:	PK Parameters

Parameter (Units)	Definition
Tmax (h)	Time of maximum observed plasma concentration
AUC(TAU) (h*ng/mL)	Area under the concentration-time curve in one dosing interval
Cmin (ng/mL)	Minimum (trough) observed plasma concentration
CLT/F (mL/min)	Apparent total body clearance

Concentration at pre-dose on Day 10 is used for C24 (Cmin) solely for the purpose of calculating AUC(TAU).

A by-participant listing of DCV PK parameter values at Day 10 is provided. Values excluded from the summary are flagged.

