Dispense Study Treatment and on-site dosing	X	X	X ^a		Study treatment should be administered in office at all study visits and after trough PK sample collection on all visits after Day 1
Assessment of Study Medication Use/Treatment Compliance		X	X	X	See Section 7.6

^a If the participant cannot attend the Treatment Week 12 visit as scheduled, the participant should complete treatment on Day 84. Treatment Week 12 assessments should be conducted once the participant returns to the site and no additional dispensing or dosing will occur on this visit. Similarly drug dispensing and dosing will not occur for those participants that discontinue early from the study

Table 2-3: Post-Treatment Long-term Procedural Outline (AI444423)

Procedure	Post-Treatment Week 4 (± 7 days)	Post-Treatment Weeks 12 and 24 (± 7 days)	Post-Treatment Weeks 48, 72, 96 (± 6 weeks)	Post-Treatment Week 108/ End of Study (± 6 weeks)	Notes
Safety Assessments					
Targeted Physical Examination	X			X	Should include assessment of heart, lung, and abdomen
Physical Measurements	X	X	X	X	Height and weight
Vital Signs	X	X	X	X	Includes body temperature, respiratory rate, and seated blood pressure and heart rate. Blood pressure and heart rate should be measured after the participant has been at rest.
Serious Adverse Events Assessment	X	X	X	X	Only SAEs related to study drug or protocol-specified procedure(s) should be reported after Post-Treatment Week 4.
Adverse Events Assessment	X				
Hepatic disease progression	X	X	X	X	Development of cirrhosis and/or its complications
Laboratory Tests	X	X	X	X	Fasting not required
Pregnancy Test FOCBP only	X				Post-Treatment Week 4 only. Urine pregnancy test; collect serum if urine is positive
Efficacy Assessments					
HCV RNA and backup HCV RNA sample	X	X	X	X	Participants with suspected relapse will have samples collected to retest HCV

Table 2-3: Post-Treatment Long-term Procedural Outline (AI444423)

Procedure	Post-Treatment Week 4 (± 7 days)	Post-Treatment Weeks 12 and 24 (± 7 days)	Post-Treatment Weeks 48, 72, 96 (± 6 weeks)	Post-Treatment Week 108/ End of Study (± 6 weeks)	Notes
HCV Resistance and backup HCV Resistance	X	X	X	X	RNA, HCV genotype, and HCV resistance at an unscheduled visit as soon as possible before their next regular visit
HCV Genotype	HCV Genotype sample to be collected at time of HCV RNA sample collection for suspected relapse to evaluate for possible re-infection/relapse				
Other Assessments					

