7.6 Treatment Compliance

Study treatment compliance will be assessed at all on-treatment study visits through review of the participant's dosing diary and drug accountability (review of used/unused study medication).

Participants [or the participant's legally acceptable representative, parent(s), or legal guardian] will be instructed to record dosing in a dosing diary and to bring unused study medication containers to each visit as well as any empty containers. The diaries will be reviewed at each visit in combination with drug accountability, and the sites should discuss any discrepancies noted.

Study drugs will be collected at all visits and new study drug may be dispensed; unused SOF will be redispensed. The dates and number of DCV tablets and SOF tablets/European Commission approved paediatric formulation dispensed and returned must be recorded on the drug accountability form maintained on-site.

On Day 10, when the serial PK sampling will be performed, treatment should be administered at the clinic and not taken at home. Likewise, on visits when trough PK samples are collected, Week 4, Week 8 and Week 12, treatment should be administered at the clinic after collection of the PK sample. The timing of the dose prior to PK sample collection should be recorded in the diary.

[REDACTED]

[Redacted text block]

[Redacted text block]

[Redacted text block]

[Redacted text block]

[Redacted text block]

[Redacted text block]

[Redacted text block]

[Redacted text block]

[Redacted text block]

[Redacted text block]

[Redacted text block]

[Redacted text block]

[Redacted text block]

[Redacted text block]

[REDACTED]

[REDACTED]

[REDACTED]

[REDACTED]

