10.3 Statistical Analyses

The statistical analysis plan will be developed and finalized before database lock and will describe the selection of participants to be included in the analyses, and procedures for accounting for missing, unused, and spurious data. Below is a summary of planned statistical analyses of the primary and secondary endpoints.

A description of the participant population will be included in the statistical output reported, including subgroups of age, gender and race.

Note: With the early termination of this study, previously collected data to address PK, SVR, and select safety assessments (e.g. AEs, laboratory tests, end of treatment subject status) will be reported only within adolescent participants 12 to <18 years of age. Given the small number of subjects enrolled in the study, no statistical analyses will be performed. Genotypic substitution(s) associated with virologic failure and the acceptability and palatability of the DCV formulations will not be reported. Likewise, an interim analysis will not be performed.

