6.7.3 Trough Concentrations

Trough concentrations of DCV and SOF/metabolites are summarized over time at each scheduled analysis visit (Day 10, Weeks 4, 8, and 12) for treated participants using univariate statistics (i.e., n, mean, SD, geometric mean, %CV, median, quartiles, minimum, and maximum).

Trough concentrations must meet each of the following criteria to be included in the statistical summary:

- Complete sampling and dosing times;
- Collected within 20-28 hours (inclusive) of the previous day's dose;
- Collected before the next dose;

Values that do not meet all the above criteria are excluded from the analysis.

Longitudinal plots display geometric mean of trough concentrations versus visit.

By-participant listings of DCV and SOF/metabolite trough concentrations are provided. Values excluded from summaries are flagged.

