- Exclusion criterion 3c: Albumin < 35 g/L or < 3.5 g/dL
- Exclusion criterion 3d: Total bilirubin > 19 μmol/L or > 1.1 mg/dL without history of Gilbert syndrome. Gilbert syndrome is identified from general medical history specify details (#);
- Exclusion criterion 3e: Alpha fetoprotein > 50 ng/mL or > 50 µg/L
- Exclusion criterion 3f: ANC $< 1.5 \times 10^9$ cells/L or $< 1.5 \times 10^3$ cells/ μ L
- Exclusion criterion 3g: Hemoglobin < 100 g/L or < 10 g/dL
- Exclusion criterion 3h: Platelets < 100 x 10⁹ cells/L
- Exclusion criterion 3i: Creatinine clearance < 1 mL/s/m² or < 60 mL/min/1.73m², using the Schwartz formula.
- (#) Non-study medications and medical conditions marked above with # are identified by a BMS physician prior to database lock.

The screening portion of the pre-treatment analysis period begins at informed consent and ends before the start of study therapy (Day 1).

[figure not shown]
A participant with multiple pre-treatment measurements (e.g., HCV RNA) is considered to have an eligibility deviation only if all pre-treatment measurements meet the deviation criterion.

Participant Management Deviations

Participant management deviations are evaluated during the on-treatment or follow-up analysis period for the following categories:

- At least 2 consecutive missed doses of DCV before Day 10 PK sampling, or at least 1 missed dose of DCV within 2 days before Day 10 PK sampling. Missed doses of DCV are identified from interruptions or gaps between dosing records;
- At least twice of DCV target daily dose taken within 2 days before Day 10 PK sampling;
- DCV or SOF average daily dose < 80% of target daily dose;
- DCV or SOF interruption > 7 consecutive days;
- Continuation of study therapy after having virologic breakthrough;
- Use of prohibited non-study concomitant medication for more than 1 day, including anti-HCV medications (#). Generic drug names are presented alphabetically as subcategories;
- Use of non-study anti-HCV medication during follow-up (#). Generic drug names are presented alphabetically as subcategories;
- (#) Non-study medications marked above with # are identified by a BMS physician prior to database lock.

Anti-HCV Medications

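### Does using the Day 10 pre-dose concentration as the 24-hour value, without the trough timing window, distort AUC(TAU) and CLT/F?

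*SAP*

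**What the plan says.** Day 10 sampling stops at 8 hours. SAP 6.7.1.1 summarizes concentrations "at each nominal collection hour: 0 (pre-dose), 30 min, 1 (Cohorts 1 and 2 only), 2, 4, and 8". To complete the 24-hour interval, SAP 6.7.2 states: "Concentration at pre-dose on Day 10 is used for C24 (Cmin) solely for the purpose of calculating AUC(TAU". The only condition attached is that the sample be pre-dose. The same section allows non-compartmental or model-based derivation as needed, and says that parameter values left out of the summary are flagged.

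SAP 6.7.3 counts Day 10 among the trough visits. For that summary it requires complete times, collection before the next dose, and "Collected within 20-28 hours (inclusive) of the previous day's dose". Values that fail are left out of the trough analysis.

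Two other places bear on the point. SAP 6.7 says "PK analysis, reporting, and exclusion criteria follow the BMS PK Harmonization Document", and adds that Section 9 of that document covers half-life exclusions and how other PK parameters are affected. SAP Appendix 1 counts as a relevant deviation "at least 1 missed dose of DCV within 2 days before Day 10 PK sampling"; such deviations are summarized, and no effect on AUC(TAU) is stated.

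**The concern.** The pre-dose value is a fair substitute for the 24-hour value when dosing is at steady state and the last dose was taken about 24 hours earlier. If that dose was late, early or missed, it is not. With no sample after 8 hours, the segment from 8 to 24 hours rests on the measured 8-hour value and the substituted one. At regular 24-hour dosing that segment is 53% to 61% of AUC(TAU) in the model used below.

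Read literally, one tube could be rejected as a 24-hour trough under 6.7.3 and accepted as the 24-hour point under 6.7.2. AUC(TAU) and CLT/F are two of the five primary PK parameters, so the accuracy and internal consistency of primary results would be at stake. The SAP foresees irregular dosing before Day 10 but does not say what follows for these two parameters.

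**Working it through.** **Which conditions are absent.** Of the three 6.7.3 criteria, collection before the next dose is already met by a pre-dose sample. Complete times and the 20 to 28 hour interval are the two not repeated in 6.7.2.

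**Inputs.** Sampling times 0, 0.5, 1, 2, 4 and 8 h (SAP 6.7.1.1). Half-life 24 h, from Protocol Appendix 4, which equates 5 days with 5 half-lives of the study drug. Assumed, because the documents do not give them: one compartment, absorption rate 1 to 1.5 per hour, linear or linear-up/log-down trapezoid, and a shorter half-life of 12 h as a sensitivity case. The plan states no figure that depends on this rule, so there is none to reproduce first.

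**Ratio of pre-dose to true 24-hour value, half-life 24 h.** By 12 h absorption is essentially over, so each dose contributes in proportion to 0.5^(t/24). Take the pre-dose level C0 in those units. Over the next 24 h it halves, and the new dose adds 0.5, so C24 = 0.5 + 0.5 × C0.

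Under the linear rule the 24-hour value carries weight 16/2 = 8 h. The share w = 8 × C24/AUC is about 0.24, and the AUC(TAU) factor is 1 + w × (C0/C24 - 1). The last column gives the full calculation over both trapezoid rules and both absorption rates.

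| Dosing before Day 10 | C0 | C24 | C0/C24 | Linear, w = 0.24 | Full range |
|---|---|---|---|---|---|
| Regular, 24 h gap | 0.5/0.5 = 1 | 1 | 1 | 1 | 1 |
| 12 h gap, earlier doses shifted too | 0.7071/0.5 = 1.414 | 1.207 | 1.17 | 1.041 | 1.040 to 1.046 |
| 12 h gap, only the last dose late | 0.7071 + 0.25/0.5 = 1.207 | 1.104 | 1.09 | 1.022 | 1.022 to 1.026 |
| Previous day's dose missed, 48 h gap | 0.25/0.5 = 0.5 | 0.75 | 0.667 | 0.920 | 0.899 to 0.922 |
| Only the Day 8 dose missed, 24 h gap | 0.5 + 0.125/0.5 = 0.75 | 0.875 | 0.857 | 0.966 | 0.959 to 0.967 |

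CLT/F moves by the inverse: 1/1.046 = 0.96 and 1/0.899 = 1.11.

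**Shorter half-lives.** Over 12 to 24 h the factors are 1.040 to 1.123 for a 12 h gap (earlier doses shifted too) and 0.802 to 0.922 for a 48 h gap. Inside the 20 to 28 h window they are 0.961 to 1.040. An assumed half-life as short as 8 h takes the extremes to about +18% and -22%.

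**Effect on a summary of five.** One affected profile moves the geometric mean by the fifth root of its factor.
- Half-life 24 h: 1.046^(1/5) = 1.009 and 0.899^(1/5) = 0.979.
- Half-life 12 h: 1.123^(1/5) = 1.023 and 0.802^(1/5) = 0.957.

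For scale, take the 35% inter-participant CV for AUC in SAP section 4. The log-scale SD is sqrt(ln(1 + 0.35^2)) = 0.340. The 95% interval for a geometric mean of five is then exp(±2.776 × 0.340/sqrt(5)), a factor of 0.66 to 1.53.

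**Can the analyst see the problem?** Yes. Protocol 7.6 provides that "The timing of the dose prior to PK sample collection should be recorded in the diary". SAP 6.7.2 and 6.7.3 list PK parameters and troughs by participant with exclusions flagged, and Appendix 1 identifies missed and doubled doses before Day 10. A mismatch between the two tables would be visible in five profiles.

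**The case for a change.** The strongest case for a change is that the SAP writes its own window for troughs and its own substitution rule for C24, so a reader expects the two to be linked there. The named parts of the sponsor document concern half-life exclusions, their effect on other parameters, and values below quantification; none is said to cover C24. A flag for excluded values does not say what triggers exclusion. One sentence would settle it, with no new data, and one profile is a fifth of the primary summary. On-site dosing does not help either: "Study treatment should be administered in office at all study visits" governs visit days and says nothing about when the dose was taken the day before.

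The textual part of this stands: 6.7.2 is silent on the two criteria. What does not follow is that the plan produces a wrong result. Exclusion criteria are expressly delegated, and Section 9 of the sponsor document deals with how exclusions carry over to other parameters. That document is not available here, so whether it covers C24 cannot be settled from the protocol and SAP. The natural remedy, model-based derivation or a flagged exclusion, is already permitted.

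A stricter rule could also cost something. Refusing C24 after any missed dose in the previous two days would reject a profile in which only the Day 8 dose was missed. Its pre-dose sample still falls 24 h after a dose, and the substitution error is -2% to -4% over half-lives of 12 to 24 h. That is no worse than the error tolerated inside the 20 to 28 h window, and a profile could be lost from a summary of five.

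**Conclusion.** No change is called for. This is a gap in wording that a pharmacokineticist fills sensibly with tools the SAP already provides.

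At the document-implied half-life of 24 h, the substitution shifts AUC(TAU) in an affected profile by +2% to +5% for a 12 h gap and by -8% to -10% after a missed dose. Larger figures need shorter, assumed half-lives. A late or missed dose also changes exposure itself, but a measured 24-hour sample would show that part too, so it is not due to the rule.

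No decision depends on the result. Protocol 10.3.6 drops the interim analysis that would have guided dosing, and Protocol 10.3 states: "Given the small number of subjects enrolled in the study, no statistical analyses will be performed". What remains is a descriptive report of already collected data in five adolescents, and neither document shows that any of them had an irregular gap before Day 10.

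The conclusion rests on the assumed one-compartment model and on reading the Appendix 4 half-life as applying to daclatasvir. It is not sensitive to the half-life. Even at 8 h, one affected profile in five would move the geometric mean by 1.177^(1/5) = 1.033 or 0.776^(1/5) = 0.951, well inside the sampling uncertainty of a mean of five.

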6.7.3 Trough Concentrations

Trough concentrations of DCV and SOF/metabolites are summarized over time at each scheduled analysis visit (Day 10, Weeks 4, 8, and 12) for treated participants using univariate statistics (i.e., n, mean, SD, geometric mean, %CV, median, quartiles, minimum, and maximum).

Trough concentrations must meet each of the following criteria to be included in the statistical summary:

- Complete sampling and dosing times;
- Collected within 20-28 hours (inclusive) of the previous day's dose;
- Collected before the next dose;

Values that do not meet all the above criteria are excluded from the analysis.

Longitudinal plots display geometric mean of trough concentrations versus visit.

By-participant listings of DCV and SOF/metabolite trough concentrations are provided. Values excluded from summaries are flagged.

6.8 Questionnaires

Questionnaires of DCV palatability and acceptability are assessed for treated participants.

A by-participant listing of DCV palatability and acceptability assessments is provided.

6.8.1 Palatability Assessment of DCV

Palatability of DCV is summarized over time at baseline and each scheduled analysis visit on treatment (Weeks 4 and 12) and by relative time (10 sec, 5 min, 10 min) in the following categories: super bad; bad; maybe good or maybe bad; good; super good; not reported (includes missing and not assessed).

6.8.2 Acceptability Assessment of DCV

Acceptability of DCV is summarized over time at baseline and each scheduled analysis visit on treatment (Weeks 4 and 12) in the following categories:

- Tablet easy to take: yes, no, and not reported. Reasons for "no" include the following subcategories: it was too big; it got stuck on tongue; other.
- Chewable tablet easy to take: yes, no, and not reported. Reasons for "no" include the following subcategories: it was too hard; it took a long time to chew; child had to drink something to help swallow the pieces; at times, the child experiences problems in chewing and swallowing; other.
- Any problems with chewable tablet packaging: yes, no, and not reported. Reasons for "no" include the following subcategories: it was difficult to push out the tablet through the packaging; the tablet broke when pushed out; the package had to be cut open; other.

7 CONVENTIONS

Conventions are followed as per the following BMS documents, unless specified otherwise: Global Biometric Sciences General Requirements for Statistical Outputs⁶; Global Standard Table Reporting Requirements Specification; Global Standard Listing Reporting Requirements Specification.

